7.3 Phase two

7.3.1 Initial Study Treatment phase (Month 0 to Month 3)

Once Screening is fully satisfied, participants will proceed to the Baseline visit. At the Baseline study staff will dispense Study Drug.

Note: Screening and baseline can occur on the same day if clinical labs (creatinine and LFTs) have been drawn as part of routine care within 3 months of the baseline.

Participants will begin use of study drug the day after baseline visit and will remain on that regimen (changes notwithstanding) for 3 months (+/- 7 days).

7.4 Phase three

7.4.1 Washout phase (Month 3 to 2 weeks-post Month 3)

At this visit participants will surrender their study drug supply and begin a two-week long washout period, after which they will return for the Crossover visit, a.k.a., 3-months plus 2-weeks, a.k.a. Visit Four.

In disputes about the timing of visits the priority must go to ensuring the participant is washed-out of the first phase of study drug use for no less than 14 days. If that gap, for any reason, must be longer, justification should be provided in the study participant's progress notes.

7.4.2 Crossover Treatment phase (Month 3 post 2-week-washout to Month 6)

At this visit, the Month 3 plus 2-weeks post-washout visit, participants will be switched to whatever study drug they did not utilize in the first three months (Sildenafil to placebo or placebo to Sildenafil).

Participants will remain in this phase, taking the crossover treatment for 3-months (+/- 7 days)

7.4.3 Termination Visit and Safety Follow-up Visit

This is the final visit of the study. It marks the 6-month time point which is the culmination of the first 3-month phase, the 2-week washout phase, and the second 3-month phase.

There are no planned visits beyond the Termination visit.

8. STUDY POPULATION

8.1 Inclusion criteria

Subjects must meet the following criteria to be eligible for enrollment in the study:

- 1) Meets 2010 American College of Rheumatology (ACR) classification criteria for diagnosis of RA (see MOOP, Appendix 2)
- 2) Aged 18 years or older
- 3) No known history of CVD (see Exclusion Criteria)
- 4) At least one traditional CV risk factor (i.e.,
 - a. older age [men \geq 45 years, women \geq 55 years],
 - b. obesity [defined as body mass index (BMI) $>$ 30 kg/m²],
 - c. smoking,
 - d. hypertension,
 - e. hyperlipidemia,
 - f. diabetes mellitus,
 - g. family history of premature [defined as diagnosed at $<$ 65 years old] CVD in first-degree relative)
- 5) On stable baseline doses of RA medications (defined as no change in dose within past 4 weeks and no anticipated changes over the next 6 months)
- 6) On no higher than 10 mg per day of prednisone or prednisone-equivalent within past 4 weeks (however, intra-articular corticosteroids are permitted)
- 7) RA disease duration (from symptom onset) of more than 6 months
- 8) Having clinical disease activity index (CDAI) of $>$ 2.8 but \leq 22 (i.e., either low or moderate disease activity), within 30 days of study enrollment

8.2 Exclusion criteria

Subjects who meet any of the following criteria will be excluded from enrollment in the study:

- 1) Aged <18 years old
- 2) Pregnant women
- 3) Known personal history of CVD: clinical diagnoses of
 - a. stroke,
 - b. transient ischemic attack,
 - c. myocardial infarction,
 - d. acute coronary syndrome,
 - e. peripheral arterial disease,
 - f. percutaneous coronary intervention
 - g. coronary bypass graft surgery
- 4) Use of high-dose statins (i.e., atorvastatin 40-80 mg/day or rosuvastatin 20-40 mg/day) currently or within past 3 months, or any dose changes of statins or of blood pressure medications that may affect endothelial function (i.e., angiotensin-converting-enzyme [ACE] inhibitors or angiotensin receptor blockers [ARBs]) within past 3 months. If on statin or an ACE-inhibitor or ARB, there should be no anticipated dose changes over the next 6 months.
- 5) Persons with intra-cardiac and intra-pulmonary shunts, unstable cardiopulmonary conditions, or anyone on chronic oxygen therapy
- 6) Persons taking nitric oxide donors, organic nitrites and nitrates, such as glyceryl trinitrate (nitroglycerin), sodium nitroprusside, amyl nitrite ("poppers")

- 7) Severe hepatic impairment (liver function tests >1.5 times upper limit of normal) within past 4 weeks
- 8) Severe impairment in renal function (serum creatinine \geq 1.5 mg/dL) within past 4 weeks
- 9) Hypotension (defined as blood pressure [BP] <90/60)
- 10) Hereditary degenerative retinal disorders (including genetic disorders of retinal phosphodiesterases)
- 11) Persons already taking (or taken within 3 months) sildenafil or other PDE inhibitors (i.e., tadalafil, vardenafil)
- 12) Persons unable to provide voluntary written informed consent
- 13) Severe hypertension (BP >170/110)
- 14) Persons with HIV/AIDS

8.3 **Justification of selection criteria**

The selection criteria were carefully selected to exclude subjects from the study who may potentially be exposed to specific risks after administering the study drug as well as subjects with conditions that may have an impact on the aims of this study.

Subjects over 65 years old will be excluded due to safety concerns regarding use of the 50 mg daily dose of sildenafil in this age group, and inability to achieve blinding with 25 mg daily dose due to altered pharmacokinetics of the drug if over-encapsulated.

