1. PROTOCOL SYNOPSIS

Title	Does Sildenafil Improve Endothelial Dysfunction in Rheumatoid Arthritis?
Short title	SEDRA
Clinical study phase	II
Study objective(s)	The primary objective of this study is to determine whether sildenafil use in rheumatoid arthritis (RA) patients leads to improvement in parameters of vascular function and to confirm its safety profile.
Test drug(s)	Sildenafil
Name of active ingredient	Sildenafil
Dose(s)	50 mg once daily
Route of administration	Oral
Duration of treatment	3 months
Reference drug(s)	Placebo
Name of active ingredient	Not applicable
Dose(s)	Matching placebo tablets to sildenafil 50 mg once daily
Route of administration	Oral
Duration of treatment	3 months
Background treatment	Not applicable
Indication	RA patients with no known history of cardiovascular disease(CVD), but at least one traditional cardiovascular (CV) risk factor in addition to their RA

Diagnosis and main criteria for inclusion	
 a. Meets 2010 American College of Rheumatology (ACR) classification criteria¹ for diagnosis of RA b. Aged 18 years or older c. No known history of CVD (see Exclusion Criteria) d. At least one traditional CV risk factor (i.e., older age [men \geq45 years, women \geq55 years], obesity [defined as body mass index (BMI) $>$30 kg/m²], smoking, hypertension, hyperlipidemia, diabetes mellitus, family history of premature [defined as diagnosed at $<$65 years old] CVD in first-degree relative) e. On stable baseline doses of RA medications, defined as no change in dose within past 4 weeks and no anticipated changes over the next 6 months f. On no higher than 10 mg per day of prednisone or prednisone-equivalent within past 4 weeks g. RA disease duration (from symptom onset) of more than 6 months h. Having clinical disease activity index (CDAI) of $>$2.8 but \leq22 (i.e., either low or moderate disease activity), within 30 days of study enrollment
Study design	6-month prospective phase II, single-center, randomized double-blind, placebo-controlled crossover single-center efficacy trial

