9.1.1 Sildenafil

Sildenafil will be supplied at 50 mg as film-coated, immediate-release tablets. Beginning May 1, 2019, sildenafil will be supplied as two 20-mg and two 5-mg tablets to equal a 50 mg dose. All study drug and placebo tablets will be provided through the UPMC Investigational Drug Service, who will also be handling patient randomization.

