9.3 Assignment – Randomization

This is a randomized, double-blind, placebo-controlled, crossover, single-center study. Subjects who complete all screening procedures and meet all the eligibility criteria are to be randomized in a 1:1 ratio by the UPMC IDS.

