9.4.1 Allocation Concealment and Blinding

The study will be blinded such that neither the investigator(s) nor the subject(s) will know the allocation assignment. To ensure enforcement of this, a biostatistician not involved with patient care will generate the treatment status randomization list using Stata (Stata Corp, USA). The randomization sequence will be kept confidential by an independent data handler. A secure password-protected electronic database will be used for eligibility confirmation and allocation assignment. Different study personnel will collect adverse event data vs. outcome data, to minimize risk of unblinding. Criteria for breaking the blinding will include adverse risk benefit profiles in either group, as determined by the Institutional Review Board and/or safety monitor.

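### Section 8.3 says subjects over 65 will be excluded for safety at 50 mg daily, but no listed eligibility criterion sets an upper age limit

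*Combined protocol and SAP*

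**What the plan says.** **Age.** Section 8.3 (Justification of selection criteria) states: "Subjects over 65 years old will be excluded due to safety concerns regarding use of the 50 mg daily dose of sildenafil". It adds a second reason: "inability to achieve blinding with 25 mg daily dose due to altered pharmacokinetics of the drug if over-encapsulated".

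The criteria themselves read differently. The synopsis asks for "Aged 18 years or older", and section 8.1, item 2, uses the same words. Section 8.2, item 1, excludes only those "Aged <18 years old". Section 8.1, item 4, requires "At least one traditional CV risk factor", and its first option is older age (men from 45, women from 55) with no upper bound.

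Section 9.3 ties randomization to these lists: "Subjects who complete all screening procedures and meet all the eligibility criteria are to be randomized". The synopsis and section 9.1 give one dose, 50 mg once daily, with no reduction for age.

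**Laboratory window.** In section 8.2, exclusions 7 (liver) and 8 (creatinine) refer to the past 4 weeks. Section 7.2.1 includes creatinine and liver function tests in the screening, but allows a same-day screening and baseline if routine results fall within 90 days of baseline. Section 7.3.1 repeats this allowance as 3 months. Section 10.2.1 accepts routine results up to 3 months before screening.

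**The concern.** A justification section should explain the criteria that exist. Here it announces an exclusion that appears in no list, and the reason given is safety at the only dose used in the trial.

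Either reading leaves something to repair. If section 8.3 states the intended rule, the lists admit people whom the protocol means to protect. If section 8.3 is a remnant, the protocol raises a safety concern about over-65s at 50 mg and then doses them without answering it.

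The laboratory point is smaller. Where an older routine result is used, exclusions 7 and 8 may be judged on a result from before the 4 weeks they specify.

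**Working it through.** The age point is a comparison of texts; only the laboratory point needs arithmetic.

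**1. The plan's own design figure.** Section 15.2 claims 80% power with 60 subjects at an effect size of 0.37, paired t-test; section 15.1 sets two-sided alpha at 0.05. The noncentral-t calculation gives 80.5%, and the exact requirement for 80% is 59.3, hence 60. With the stated SD of about 4, 0.37 × 4 = 1.48, which matches the stated 1.5%. The figure reproduces. Age is not an input to it, so settling the age rule changes no stated sample-size number.

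**2. Age rules side by side.**
- Synopsis: 18 or older; no upper limit.
- Section 8.1, item 2: the same.
- Section 8.1, item 4: older age counts as a risk factor, without an upper bound. Anyone over 65 therefore meets this item on age alone, and it screens none of them out.
- Section 8.2, items 1 to 14: under 18 excluded; no upper age in any item.
- Section 8.3: over 65 to be excluded.
- Section 9.3: randomize those who meet the criteria.

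Take a subject aged 70 who meets every other criterion. Sections 8.1, 8.2 and 9.3 lead to randomization; section 8.3 says the subject is excluded. Nothing in the readable text says which prevails.

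**3. Number affected.** Up to 80 subjects are to be randomized, but no expected age distribution is given. No count or percentage of over-65s can be derived.

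**4. Laboratory age at baseline**, taking 3 months as 90 days:
- Window in exclusions 7 and 8: 4 × 7 = 28 days.
- Same-day route: up to 90 days, which is 90 − 28 = 62 days beyond that window.
- Separate visits: up to 90 days at screening plus up to 28 days to baseline (section 10.1), so at most 90 + 28 = 118 days, or 118 − 28 = 90 days beyond it. This needs both maxima at once.

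The blood list for the baseline visit (section 10.2.2) contains neither creatinine nor liver function tests. The reconfirmation of eligibility there applies only when screening and baseline are separate visits. No listed baseline test would therefore detect a change since the routine draw.

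**The case against.** The operative text is uniform. The synopsis and sections 8.1 and 8.2 agree, and randomization follows the criteria. The outlier is one sentence in a rationale section, which may be a remnant of an older design. This stands as far as it goes: the age range is not undefined, and the repair may be a deletion. But the documents do not show that the sentence is a remnant, and its wording is declarative.

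Harm is not shown either. Section 9.4.1 says that an "electronic database will be used for eligibility confirmation and allocation assignment"; neither that database nor the manual of operations is in the documents. Staff may already apply a limit of 65, or may not. A reader might infer that over-65s have been enrolled against the protocol's own safety rule; the documents do not support that.

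Some safeguards apply at any age: exclusions for hypotension and for hepatic and renal impairment, automatic withdrawal for blood pressure below 80/50, withdrawal on the investigator's judgement, and reporting of serious events to the independent safety officer within 48 hours. They reduce the risk but do not answer a concern that the protocol ties to age and dose.

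A reader might also infer that the blinding reason in section 8.3 is obsolete because, from May 2019, "sildenafil will be supplied as two 20-mg and two 5-mg tablets to equal a 50 mg dose". Section 9.1.1 describes only the 50 mg dose. Nothing in the documents offers or discusses a blinded 25 mg regimen, so the inference is speculation. It would in any case leave the safety reason untouched.

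On laboratory results, one can read exclusions 7 and 8 as defining the condition and section 10.2.1 as defining acceptable evidence. The allowance appears in three sections, so it looks deliberate. That reading is reasonable, but a result 3 months old still cannot show the state of the past 4 weeks.

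**Conclusion.** The contradiction is real, and nothing in the readable text resolves it: following the listed criteria can admit subjects over 65, whom section 8.3 says to exclude on safety grounds at the dose everyone is assigned. It is an internal inconsistency that should be fixed. A stronger rating is not supported, because the number of over-65s and the checklist that staff use are both unknown, and no analysis or sample-size figure depends on the answer. The conclusion does not depend on which text the sponsor intended.

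The laboratory mismatch is also real, but minor and secondary. It arises only when older routine results are used in place of a screening draw.

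**What to change.** **Age.** The sponsor should state which text is intended.
- Unless section 8.3 is confirmed as leftover, add *aged >65 years at randomization* to section 8.2, and the matching upper limit to section 8.1 and the synopsis. The time point matters: section 8.4 withdraws anyone who develops an exclusion criterion other than number 4, and section 8.5 allows no replacement. An undated limit could therefore force out subjects who pass 65 during the trial.
- If it is leftover, delete the sentence and add a justification for 50 mg daily in over-65s.

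**Laboratory window (minor).** Use one window in sections 7.2.1, 7.3.1, 8.2 and 10.2.1, including the re-screening paragraph of 10.2.1. The 4 weeks already in exclusions 7 and 8, counted back from baseline, is preferable, with a repeat draw when routine results are older. If the sponsor prefers 90 days, exclusions 7 and 8 should say so.

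**Cost.** A short amendment and an updated eligibility checklist; somewhat slower recruitment if the age limit is kept; some repeat screening draws if the 4-week window is kept.

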8.4 Withdrawal of Subjects

Subjects *must* be withdrawn from the study for the following reasons:

- At their own request or at the request of their legally acceptable representative
At any time during the study and without giving reasons, a subject may decline to participate further. The subject will not suffer any disadvantage as a result.
- Development of any of the exclusion criteria except for #4 (new or changed doses of CV and RA medications will be documented and addressed via statistical adjustment).
- If, in the investigator's opinion, continuation of the study would be harmful to the subject's well-being
- Occurrence of AEs or inter-current diseases which the investigator judges unacceptable for continuation of participation in the study
- Pre-specified stopping rules for adverse events: Participants will be automatically withdrawn from the trial if any of the following adverse events occurs: hypotension with BP < 80/50, myocardial infarction, non-arteritic ischemic optic neuropathy, retinal hemorrhage, sudden hearing loss, priapism (prolonged penile erection), and pregnancy.
- Occurrence of adverse drug reactions, which in the investigator's opinion have a negative impact on the subject's individual risk-benefit ratio.
- Non-compliance with the conditions for the trial or instructions by the investigator
- Although not preferred, subjects may interrupt their intake of study medication for reasonable circumstances/reasons at any time (e.g., hospitalization in a remote hospital without study medication access, safety reasons, and side effects). If study medication nonadherence is >50% by pill counts, or if the nonadherence is for 14 or more consecutive days before the study visit, the subject must be withdrawn. In case treatment requires interruption for > 3 days and ≤ 14 consecutive days before the study visit, it is at the discretion of the investigator if the study medication can be restarted. However, any study medication nonadherence will be documented, and interruption of medication use for 3-45 days will be recorded as a protocol deviation.
- In case of pregnancy or breast feeding.

- In case the subject does not tolerate the drug.

8.5 Replacement of Withdrawn Subjects

There will be no replacement of randomized subjects who withdraw from the study.

For withdrawn subjects, certified return receipt of drug will be requested by mailing postage-paid mailers to the subjects, after at least three call attempts.

8.6 Subject Identification

After a subject signs the informed consent form, a subject identification number will be created. This will be a unique code composed of study name and subject number

First 5 letters = SEDRA (to identify with this trial)

Last 4 digits = Unique subject number (chronologically entered in Recruitment and Screening Log)

									

									
									
PARTICIPANT IDENTIFICATION									

Within the Rheumatic Disease Management System (RDMS) electronic research database, each study subject will be assigned a random 9-digit study ID number, which will be used for source documents, blinded study drug dispensation, etc.

8.7 Study Population Demographics

The following demographic data will be recorded:

- Date of birth (month and year) (age)
- Sex
- Race/Ethnicity
- Socioeconomic data
- Education level
- Emergency Contact
- Mailing address

- Contact information
- Medical History - A medical history will be collected by study personnel including all active conditions (and corresponding organ systems) and non-active conditions (and corresponding organ systems) going back one year.

9. TREATMENT

9.1 Study drug

Test Drug: Sildenafil

Dosage: 50 mg

Route of administration: oral

Time and frequency of administration: once daily

9.1.1 Sildenafil

Sildenafil will be supplied at 50 mg as film-coated, immediate-release tablets. Beginning May 1, 2019, sildenafil will be supplied as two 20-mg and two 5-mg tablets to equal a 50 mg dose. All study drug and placebo tablets will be provided through the UPMC Investigational Drug Service, who will also be handling patient randomization.

9.1.2 Matching placebo

Matching placebo tablets will appear identical to active sildenafil tablets but will not contain active study drug.

9.2 Justification of study drug selection

This dose was chosen because it is the usual dose used and FDA-approved for the treatment of erectile dysfunction (ED), with a known favorable safety profile at that dose. Furthermore, this was the dose used in a double-blind, placebo-controlled, prospective trial of 24 men with type 2 diabetes with ED, wherein it was shown that daily use of sildenafil 50 mg/day for 10 weeks resulted in improved endothelial function as measured by brachial arterial FMD.

Sildenafil 50 mg orally once daily for 3 months will be provided in bottles during the sildenafil treatment periods.

Placebo pills with the same size, shape, color, and texture as sildenafil will also be provided in bottles, to be taken orally once daily for 3 months during the placebo periods.

9.3 Assignment – Randomization

This is a randomized, double-blind, placebo-controlled, crossover, single-center study. Subjects who complete all screening procedures and meet all the eligibility criteria are to be randomized in a 1:1 ratio by the UPMC IDS.

9.4 Blinding

The study will be conducted in double-blind fashion. Active sildenafil and placebo tablet formulations will be identical in appearance (size, shape, color) and smell. The packaging and labeling will be designed to maintain blinded conditions for the investigator and the study team. The study data will remain blinded until database lock.

9.4.1 Allocation Concealment and Blinding

The study will be blinded such that neither the investigator(s) nor the subject(s) will know the allocation assignment. To ensure enforcement of this, a biostatistician not involved with patient care will generate the treatment status randomization list using Stata (Stata Corp, USA). The randomization sequence will be kept confidential by an independent data handler. A secure password-protected electronic database will be used for eligibility confirmation and allocation assignment. Different study personnel will collect adverse event data vs. outcome data, to minimize risk of unblinding. Criteria for breaking the blinding will include adverse risk benefit profiles in either group, as determined by the Institutional Review Board and/or safety monitor.

9.4.2 Emergency Unblinding

In case of emergency, the investigator is permitted to unblind individual cases. However, this will be restricted to cases of emergency where the unblinding result is of importance for the acute treatment strategy. The occurrence of an SAE should not routinely precipitate the immediate unblinding of the

label. Date, time, and reason for unblinding will be captured. Unblinding will be coordinated through the Investigational Drug Service.

9.5 Drug logistics and Accountability

Drug logistics and accountability

